#### **4.1.4        Pharmacokinetic-Evaluable Population**

Not applicable.

#### **4.1.5        Safety Population**

The Safety Population will include all enrolled patients who received any ocrelizumab. All safety analyses will use this population.

### **4.2            ANALYSIS OF STUDY CONDUCT**

The following will be summarized:

- Numbers of patients in each of the ITT, mITT, PP, and safety populations, and protocol deviations leading to exclusion from the PP population
- Number of patients who complete study treatment
- Reasons for study treatment discontinuation (separate summary of number and percentage of patients who continued onto commercial OCR for patients under protocol version 5 and patients under previous versions)
- Reasons for study discontinuation (separate summary of number and percentage of patients who continued onto commercial OCR for patients under protocol version 5 and patients under previous versions)
- Number of patients who complete 1, 2, 3, and 4 doses (dose 1 is split to two infusions and will be counted as 1 dose)
- Summary and Kaplan-Meier plots of time to discontinuation of study treatment (patients did not reach week 96)

### **4.3            ANALYSIS OF DEMOGRAPHICS AND BASELINE CHARACTERISTICS**

The following demographic and baseline characteristics will be summarized:

**Ocrelizumab—Genentech, Inc.**

17/Statistical Analysis Plan MN30035

- Age at first dose (< 40,  $\geq$  40, also < 18, 18- 40, 40-55,  $>$  55, and continuous)
- Sex
- Self-reported race and ethnicity
- Female and male reproductive statuses
- Country (USA, Canada)
- Height, weight, and BMI

History of MS summaries will include:

- Duration since MS first symptoms (in years): continuous and categorical ( $\leq$  3 years,  $>$ 3 - 5 years,  $>$ 5 - 10 years,  $>$ 10- $\leq$ 12 years,  $>$ 12 years)
- Duration since RRMS diagnosis (in years): continuous and categorical ( $\leq$  2 years,  $>$ 2 - 5 years,  $>$ 5 - 10 years,  $>$ 10- $\leq$ 12 years,  $>$ 12 years)
- Baseline EDSS: continuous and categorical ( $<$ 4 years,  $\geq$ 4 years, and  $<$ 2.5 years,  $\geq$ 2.5 years)
- Time since first MS relapse: continuous and categorical ( $\leq$ 3 months,  $>$ 3 to  $\leq$ 6 months,  $>$ 6 months)
- Qualifying events for enrollment (relapse, T1 Gd-enhanced lesion or new and/or enlarging T2 lesion)

History of prior MS treatment summaries will include:

- Number and percent of patients taking previous unique DMTs, by number and by name of DMT
- Number and percent of patients switching previous DMTs
- Duration of previous DMT (months) by name of DMT
- Reason for discontinuation from each previous DMT by name of DMT
- Number and percent of patients taking last DMT before study enrollment by name of DMT

- Duration between end of last DMT to initiation of ocrelizumab treatment: continuous (months) and categorical ( $\leq 1$  months,  $> 1$  to  $\leq 3$  months,  $> 3$  months), and by name of DMT.
- Baseline MRI results: number of Gd-enhancing T1 lesions (0, 1, 2, 3,  $\geq 4$ ) and normalized brain volume

General non-MS medical history and baseline conditions

- Study sites (number and percent of patients)

#### **4.4 EFFICACY ANALYSIS**

Efficacy endpoints will be evaluated for the mITT or ITT population as specified. Sensitivity for primary endpoint will be conducted for the PP population.

For all change from baseline analyses, except for EDSS, baseline will be defined as the last non-missing value on or before the first infusion. Unless otherwise specified, the baseline EDSS will be defined as (1) the last non-missing value on or before the first infusion, for patients who were administered only one EDSS evaluation before the first infusion, or (2) the average of the 2 EDSS results pre infusion, for patients who were administered an additional evaluation in cases where the screening EDSS was more than 14 days prior to the first infusion.

The baseline EDSS will be rounded to the second decimal point. For analyses that stratify by analysis baseline EDSS i.e. ( $< 2.5$  vs.  $\geq 2.5$ ), the EDSS values will be rounded to the nearest one decimal value.

Per protocol, unscheduled MRI evaluations conducted for suspected PML will not be included in the analysis of efficacy endpoints.

Visit windows (defined in Module 2) will be applied to key efficacy assessments to accurately capture the timing of assessment.

##### **4.4.1 Primary Efficacy Endpoint**

The proportion of patients who are free from a protocol-defined event during a 96-week period will be calculated and presented along with a two-sided 95% Clopper-Pearson exact confidence interval. Data from unscheduled visits within each respective 24-week interval will be included in the evaluation of the endpoint. Analyses will be performed for the mITT population. Patients are considered to have a protocol-defined event during the 96-week period if they discontinue due to lack of efficacy or death despite without a protocol-defined event as defined below.

#### **Event definition and Handling of Missing Data**

The definition of a protocol-defined event is the occurrence of at least one of the following while on treatment with ocrelizumab:

- A protocol-defined relapse defined as an occurrence of new or worsening neurological symptoms attributable to MS. Symptoms must persist for > 24 hours and should not be attributable to confounding clinical factors (e.g., fever, infection, injury, adverse reactions to medications), and immediately be preceded by a stable or improving neurological state for least 30 days.
- A T1 Gd-enhanced lesion on brain MRI
- A new and/or enlarging T2 lesion on brain MRI
- Confirmed disability progression (24 weeks)

The new or worsening neurological symptoms must be accompanied by objective neurological worsening consistent with an increase of at least half a step on the EDSS scale, or two points on one of the appropriate Functional Systems Score (FSS), or one point on two or more of the appropriate FSS. The change must affect the selected FSS (i.e., pyramidal, ambulation, cerebellar, brainstem, sensory, or visual). Episodic spasms, sexual dysfunction, fatigue, mood change or bladder or bowel urgency or incontinence will not suffice to establish a relapse.

Progression is defined a  $\geq$  1-point increase in EDSS score from a baseline EDSS score of 0.0–5.5 inclusive, and a 0.5-increase from a baseline EDSS score higher than 5.5.

For example, for a patient with a baseline EDSS score of 5.25 or 5.5, the progression is defined as an EDSS score of at least 6.5. For a patient with a baseline EDSS score of 5.75 or 6.0, the progression is defined as an EDSS score of at least 6.5.

Confirmation of the 24-week disability progression must occur at the regularly scheduled visit that is at least 24 weeks (168 days  $\pm$  14 days) after initial progression.

If a patient has a missing EDSS at the scheduled visit occurring at least 168 days after an initial progression, the next immediate scheduled or unscheduled EDSS will be used to confirm disability progression. In cases where confirmation of disability progression during the study is not possible due to missing 24-week assessments, such that establishment of the occurrence of a protocol-defined event is not possible, the patient will be considered as not having an event.

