4.5.6 Assessment of Disability

Disability in MS will be measured by the EDSS. See [Appendix 1](#) (schedule of activities) for the timing of these assessments. It is strongly recommended that the same EDSS rater is used for each patient throughout the study when possible. The EDSS should be done on the same day or within 24 hours prior to the study drug infusion if both are done at the same visit.

The EDSS is based on a standard neurological examination, incorporating seven functional systems (pyramidal, cerebellar, brainstem, sensory, bowel and bladder, visual, and cerebral [or mental], plus “other”) rated and scored as FSSs. Each FSS is an ordinal clinical rating scale ranging from 0 to 5 or 6. These ratings are then used in conjunction with observations and information concerning ambulation and use of assistive devices to determine the EDSS score. The EDSS is a disability scale that ranges in 0.5-point steps from 0 (normal) to 10 (death) (see [Appendix 3](#)).

Ocrelizumab—Genentech, Inc.
37/ Protocol MN30035, Version 5

Disability progression is defined as a \geq 1-point increase in EDSS score from baseline if the baseline EDSS score is between 0.0 and 5.5 (inclusive) or a 0.5-increase from baseline if the baseline EDSS score is higher than 5.5. The increase of disability progression on EDSS should be confirmed 24 weeks after the time at which the increase has been observed. The initial increase in EDSS can occur at any visit during the 96-week study.

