
Appendix 1

Schedule of Activities

Visit Number	Screening	Treatment Period						Safety Follow-up Visit^b	Early Withdrawal Visit ^c	Unscheduled Visit (due to relapse) ^d
	1	2	3	4	5	6	7			
Week	-4 ^a	-	2	24	48	72	96			
Study Day (window in days)	-28	1 Baseline	15 (± 2)	169 (± 14)	337 (± 14)	505 (± 14)	673 (± 14)			
Informed consent ^e	x									
Medical history and demographic data ^f	x									
Review inclusion and exclusion criteria	x	x								
Physical examination ^g	x	x	x	x	x	x	x	x	x	
Height	x									
Weight	x									
Vital signs ^h	x	x	x	x	x	x	x	x	x	
Laboratory Assessments ⁱ										
Hematology, chemistry, urinalysis ^j	x	x ^k		x	x	x	x	x		
Pregnancy test ^l	x	x	x	x	x	x	x	x		
Hepatitis screening ^m	x									
Hepatitis B virus DNA test ^m	x			x	x	x	x	x		
Lymphocyte subtypes ⁿ	x			x	x	x	x	x		
EDSS score	x	x ^k		x ^o	x ^o	x ^o	x	x	x	
Neurological examination ^p	x	x	x	x	x	x	x	x	x	
Patient-Reported Outcome Assessments ^q		x		x	x	x		x		

Ocrelizumab—Genentech, Inc.
75/ Protocol MN30035, Version 5

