#### 2.2.2 Secondary Efficacy Outcome Measures

- The proportion of patients free from a protocol-defined event during a 24-week period and a 48-week period
- Time to protocol-defined event (as defined in [Section 2.2.1](#) above)
- The time to onset of first relapse
- Time to onset of first T1 Gd-enhanced lesion
- Time to onset of first new and/or enlarging T2 lesion
- Time to onset of confirmed disability progression for at least 24 weeks during the study period
- Annualized relapse rate at week 96
- Total number of T1 Gd-enhanced lesions detected by brain MRI at weeks 24, 48, and 96
- Total number of new and/or enlarging T2 lesions detected by brain MRI at weeks 24, 48, and 96

- Change in total T2 lesion volume detected by brain MRI from baseline to weeks 24, 48, and 96

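### SAP 4.4.1 can count two separate transient EDSS rises as 24-week confirmed disability progression: scores in between carry no condition, and the missing-visit fallback accepts a relapse-visit score

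*SAP*

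**What the plan says.** Protocol 4.5.6 sets two conditions: "The increase of disability progression on EDSS should be confirmed 24 weeks after the time at which the increase has been observed", and "The initial increase in EDSS can occur at any visit during the 96-week study".

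SAP 4.4.1, under its heading on event definition and missing data, makes this operational. "Confirmation of the 24-week disability progression must occur at the regularly scheduled visit that is at least 24 weeks" (168 days, with a 14-day tolerance) after the initial progression. A missing-data exception follows: "If a patient has a missing EDSS at the scheduled visit occurring at least 168 days after an initial progression", then "the next immediate scheduled or unscheduled EDSS will be used to confirm disability progression". If missing assessments make confirmation impossible, the patient counts as having no event.

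SAP 2.2.2 names the secondary endpoint "Time to onset of confirmed disability progression for at least 24 weeks during the study period". SAP 4.4.2 dates it to the initial progression. SAP 4.4.1 also brings data from unscheduled visits into the primary endpoint.

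Neither document says what happens to EDSS scores between the first rise and the confirming visit. Neither bars a score taken during or soon after a relapse from serving as onset or as confirmation.

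**The concern.** The endpoint is meant to capture worsening that lasts at least 24 weeks. A rule that compares only two time points does not test that. A patient who worsens, recovers and worsens again can satisfy it, and the onset is then dated to an episode that resolved.

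The fallback adds a second route. The only unscheduled visit in the protocol's schedule (Appendix 1) is the one for relapse, so an unscheduled confirming score may be one measured during an acute attack.

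At stake is mainly the Kaplan-Meier estimate of time to CDP. The study has a single arm, so no control group carries the same misclassification. CDP is also one of the four components of the primary endpoint.

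**Working it through.** The plan gives no expected CDP rate, no rate of missed EDSS and no rate of EDSS at relapse visits. There is therefore no plan figure on this point to reproduce. What can be checked is how the rule behaves on the visit schedule.

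Inputs:
- Scheduled post-baseline EDSS on Days 169, 337, 505 and 673, each with a 14-day window (Protocol Appendix 1).
- Shortest interval that confirms: 168 − 14 = 154 days (SAP 4.4.1).
- Onset possible at any visit (Protocol 4.5.6).
- Confirming visit: the first scheduled day d with d − onset ≥ 154.

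**Onset at an on-time scheduled visit.** 337 − 169 = 505 − 337 = 673 − 505 = 168. The next visit confirms, and no scheduled score lies in between. An onset at Week 96 has no later visit.

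**Onset at an unscheduled visit between Weeks 24 and 48.** Possible onset days are 170 to 336, that is 167 days. Day 337 can confirm only if onset is on or before 337 − 154 = Day 183, which covers 14 days. For the other 167 − 14 = 153 days (153/167 = 92%), confirmation falls at Day 505, and the Day 337 score has no stated role.

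**Unscheduled onset over the whole study.** Days 2 to 672, less the three scheduled days, give 671 − 3 = 668 days. Onsets after Day 673 − 154 = 519 cannot be confirmed: 672 − 519 = 153 days. That leaves 668 − 153 = 515. Each of the four intervals between visits has 14 days with no score in between, 4 × 14 = 56. So 515 − 56 = 459 days have one (459/515 = 89%). If the 14-day tolerance is not applied, it is all 501 confirmable days.

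**Example.** A rise of 1.0 at an unscheduled visit on Day 230; back to baseline at Day 337 (337 − 230 = 107 days, too early to confirm); a rise of 1.0 again at Day 505 (505 − 230 = 275 days). On the SAP text this is CDP with onset on Day 230.

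**Shifted visits.** The windows allow a gap as short as (337 − 14) − (169 + 14) = 140 days. Any gap under 154 days moves confirmation one visit later and leaves a scheduled score in between.

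**Fallback.** Take onset at Day 169, no EDSS at Week 48, and a relapse visit on Day 400 with the score raised (400 − 169 = 231 days). That score confirms, and a return to baseline at Day 505 would not undo it.

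**Weight in the primary endpoint.** If 600 patients are analysed (an assumption, since the mITT set may be smaller), one reclassified patient moves the proportion by 1/600 = 0.17 percentage points, against a planned half-width of 4 points.

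**The case against.** The strongest reply is that the SAP does what Protocol 4.5.6 asks, which is confirmation 24 weeks later, and that silence on the scores in between is not an instruction to disregard them. SAP Appendix 3 refers to further data handling rules in DAP Module 2, which is not available here and might settle the matter. That stands as a caution. A rule this central to a named endpoint should nevertheless be in the SAP itself, and the fallback wording is explicit rather than silent.

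Four stronger readings are tempting, and the documents do not support them:

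- A reader might infer that any transient relapse worsening becomes CDP. It does not: a second raised score about 24 or more weeks later is always needed.
- A reader might see a contradiction between "Confirmation of the 24-week disability progression must occur at the regularly scheduled visit" and the fallback. It is a default followed by a missing-data exception. An unscheduled score confirms only when the scheduled one is missing, and the next score may well be a routine one.
- The 92% and 89% are shares of possible onset days, given an unscheduled onset. They are not shares of patients or of CDP events.
- Assuming a CDP rate and a number misclassified would give a percentage error, but the documents supply neither figure.

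It may also be said that the schedule does not clearly mark an EDSS at the relapse visit. SAP Appendix 3 derives relapses from EDSS at unscheduled visits, so such scores are expected.

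Finally, extra CDP events lower the event-free proportion, so the present rule works against ocrelizumab and the repair works in its favour. That is correct, and it is why the repair should be reported alongside the present rule.

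**Conclusion.** The point holds as a gap in the CDP definition. On the text of SAP 4.4.1, two separate transient rises with recovery between them can be labelled 24-week CDP and dated to the first, and a score from an acute relapse can confirm when the scheduled EDSS is missing. The exposure lies with unscheduled onsets, shifted visits and missed confirming visits, not with on-time scheduled onsets.

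The effect falls mainly on time to CDP. The primary endpoint is largely protected, because a protocol-defined relapse or any qualifying MRI lesion already makes the patient an event. It changes only where there is neither, for example where the worsening was put down to fever or infection and so failed the relapse criteria. The number of affected patients cannot be computed from the documents. The conclusion assumes that DAP Module 2 contains no rule that closes the gap.

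**What to change.** Amend SAP 4.4.1, and apply the change to both the primary endpoint and time to CDP:

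- (a) Require every non-missing EDSS between the initial rise and the confirming visit to meet the progression threshold. If one falls below it, restart from the next rise. In the Day 230 example, onset would restart at Day 505 and need confirmation at Day 673.
- (b) When the scheduled confirming EDSS is missing, use the next EDSS that is not from a relapse visit and not within 30 days after the onset of a reported relapse. Thirty days is the interval SAP Appendix 3 already uses to separate relapses.

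The cost is SAP wording and programming on data already collected, with no change to patient procedures. The downside is that a few progressions become unconfirmed and count as no event, which slightly raises the event-free proportion. Report how many, and show the result under the SAP's present rule as a sensitivity analysis. If DAP Module 2 already contains such a rule, move it into SAP 4.4.1.

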#### **4.4.2 Secondary Efficacy Endpoints**

The mITT population will be used for secondary efficacy endpoints of the proportion of patients free from a protocol-defined event during the first 24-week and 48-week period.

Analyses of all other secondary efficacy endpoints will be performed using the ITT population.

The proportion of patients free from a protocol-defined event during the first 24-week and 48-week will be presented along with a two-sided 95% Clopper-Pearson exact confidence interval. Same analysis method of the primary efficacy endpoint will be applied to the 24-week and 48-week outcomes. Note that event during the first 24-weeks will not include CDP events due to no confirmatory EDSS score can be observed within the first 24-weeks. A histogram of the percent of patients who are event free at weeks 24, 48, and 96 will be produced.

### **Time-to-event endpoints**

The Kaplan–Meier method (i.e., the product limit estimator) will be used to estimate the time to onset of the 5 parameters listed below. Kaplan-Meier plots will be produced. The event-free probability at Week 96 will be calculated based on Kaplan-Meier method as sensitivity analyses of the primary endpoint, proportion of patients without a protocol-defined event.

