#### Time to protocol-defined event

For patient with an event, it will be defined as the earliest onset time of the following: a protocol-defined relapse, T1 Gd-enhanced lesion, new and/or enlarging T2 lesion, or confirmed disability progression (see below for the determination of the time to onset of confirmed disability progression)

Patients without an event (either during the complete 96-week study period, or before early withdrawal from treatment) will be censored at the last evaluation of a protocol defined event, i.e. the maximum time of last MRI or EDSS evaluation

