#### Time to onset of first T1 Gd-enhanced lesion

For patient with event, it will be defined as the first time a T1 Gd-enhanced lesion was detected post baseline.

Patients without an event will be censored at the last performed MRI evaluation.

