## **Appendix 4** **Programming Codes for Statistical Analyses**

Kaplan-Meier method

```
proc lifetest data=dataset method=km conftype=loglog outsurv=surv  
plots=none notable STDERR;  
    time aval*eventyn(1);  
run;
```

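### The Week 96 Kaplan-Meier sensitivity analysis has no stated time scale or reading day and, as its event and censoring times are written, is biased by visit timing

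*SAP*

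**What the plan says.** SAP 4.4.2, Time-to-event endpoints, plans a product-limit estimate and adds: "The event-free probability at Week 96 will be calculated based on Kaplan-Meier method as sensitivity analyses of the primary endpoint".

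The times that enter it are defined in the subsections that follow:

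- Composite event, with 24-week progression as the fourth component: "it will be defined as the earliest onset time of the following: a protocol-defined relapse, T1 Gd-enhanced lesion, new and/or enlarging T2 lesion".
- T1 lesion: "it will be defined as the first time a T1 Gd-enhanced lesion was detected post baseline". T2 lesions are also timed at first detection.
- No composite event: the patient "will be censored at the last evaluation of a protocol defined event, i.e. the maximum time of last MRI or EDSS evaluation".
- Lesion endpoints: "Patients without an event will be censored at the last performed MRI evaluation".

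The Appendix 4 code names one time variable ("time aval*eventyn(1") and gives no evaluation day. SAP 4.4 adds: "Visit windows (defined in Module 2) will be applied to key efficacy assessments to accurately capture the timing of assessment". Module 2 was not supplied.

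Scans are scheduled only at Weeks 24, 48 and 96 (Protocol Appendix 1). The nominal Week 96 visit is Day 673, with 14 days allowed either side.

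The primary analysis uses the mITT population (SAP 4.4.1). The other sensitivity analyses use PP and mITT (SAP 4.4.4). Time to protocol-defined event falls under the ITT rule in SAP 4.4.2, so this is the only check on the primary endpoint in the full ITT population.

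**The concern.** Kaplan-Meier estimation works when censoring is unrelated to when events become visible. Here the two are tied. A lesion that forms after the Week 48 scan is normally first seen at the Week 96 scan. A patient with no event leaves the risk set at that same visit.

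If actual dates are used, the answer depends on the reading day. Read at the nominal day, the curve omits events found at visits later in the window. Read at the end of the window, it includes them, but divides each by a risk set already thinned by event-free patients with earlier visits. The primary proportion counts every Week 96 finding once and has neither problem.

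The mITT population drops patients who stop treatment early without an event, other than for death or lack of efficacy. A full-ITT estimate is the natural place to look for the effect of that exclusion. A visit-timing artefact of several points could be mistaken for it.

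**Working it through.** **Benchmark.** The documents give no figure for this estimate. The relevant planned figure is the 4-point half-width in Protocol 6.1. The simple formula gives 1.96² × 0.45 × 0.55 / 0.04² = 594.2. The exact binomial calculation with 80% assurance and a Wald interval gives n = 598, against the stated 598.86. So 4 points is a fair yardstick.

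**Inputs from the documents.** Event-free proportion p = 0.45; Week 96 window Days 659 to 687 (687 − 659 + 1 = 29 days); event and censoring rules as above.

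**Assumptions, not in the documents.** A share q of all patients has its first event detected at the Week 96 visit. Visits are spread evenly over the window. Scan and EDSS fall on one day. There is no dropout.

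**Formula.** The curve enters the window at S0 = p + q. Of the patients seen on any day, a fraction h = q / (p + q) have the event and the rest are censored. With j days of the window left, counting the current one, 1/j of those at risk are seen that day, so the curve is multiplied by (1 − h/j).

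- At Day 673 (15 days used): S0 × the product of (1 − h/j) for j = 29 down to 15.
- At Day 687 (all 29 days used): the same product for j = 29 down to 1.

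For q = 0.10: S0 = 0.55 and h = 0.10/0.55 = 0.1818. At Day 673, 0.55 × 0.878 = 0.483. At Day 687, 0.55 × 0.4725 = 0.260. A simulation of 600 patients gave 0.483 and 0.261.

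| q | S0 | h | Day 673 | Day 687 |
|---|---|---|---|---|
| 3% | 0.48 | 0.0625 | 0.459 | 0.374 |
| 7% | 0.52 | 0.1346 | 0.472 | 0.300 |
| 10% | 0.55 | 0.1818 | 0.483 | 0.260 |
| 17% | 0.62 | 0.2742 | 0.510 | 0.195 |

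Against 0.45, that is about 1 to 6 points too high at Day 673 and about 8 to 26 too low at Day 687.

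**Other visit patterns.** Simulations with q from 3% to 15% also used visits clustered around Day 673 or Day 677 (SD 5 days). Over all patterns the range was 0.458 to 0.560 at Day 673 and 0.152 to 0.371 at Day 687.

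**Scan before EDSS.** Censoring uses the later of the two dates. If the scan comes first, event-free patients stay at risk beyond their scan. With q = 11% and the scan 0 to 14 days before the EDSS, simulation gave 45.9% at Day 673 and 37.1% at Day 687, against 48.6% and 24.6% with no lag. Over q from 3% to 17%, the Day 673 bias is about 0 to 2 points.

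**Nominal times.** With every Week 96 assessment at Day 673, the curve at that day is S0 × (1 − h) = (p + q) × p/(p + q) = p, exactly 0.45. Read at Day 672 (96 × 7) on the same scale, it is still S0, which is 0.48 to 0.62 over the same range of q. Even with windowing, the reading day has to be stated.

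**The case against.** A reader might infer that the analysis is definitely run on actual visit dates. The documents do not establish that. SAP 4.4 applies visit windows from Module 2, and Appendix 3 places further data handling rules there. The Appendix 4 code does not say how its time variable is derived. If Module 2 maps these times to nominal days and the curve is read at the right one, the problem disappears. But the SAP says only that windows apply to assessments, not that event and censoring times become nominal.

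A reader might also infer that late events are always missed, or that an error of up to 26 points is planned. Late events are missed only at Day 672 or 673. At Day 687 the bias reverses, and no section proposes reading there.

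The calculation also favours a large effect. Relapses are dated at reported onset and progression at its first observation, and a first progression at Week 96 cannot be confirmed. So mainly MRI findings cluster at the last visit. The Week 96 share is assumed; at 3% the Day 673 bias is under 1 point.

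Nor would a gap from the primary necessarily be read as a dropout effect. The two analyses already differ in population, and the primary counts discontinuation for lack of efficacy or death as an event while the Kaplan-Meier definition does not. The PP analysis, drawn from ITT, also keeps some event-free dropouts.

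Finally, the study is single-arm and mostly descriptive, the primary proportion is unaffected, and no decision rule uses this estimate. All of this limits the size and consequence of the point. It does not supply the missing time scale or reading day.

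**Conclusion.** The concern holds conditionally. The written event and censoring rules, applied to actual dates, produce an estimate that does not target the primary proportion even with complete follow-up. Only a mapping to nominal visits in Module 2, with a matching reading day, would remove this, and the SAP does not state one.

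The size depends on assumptions. With evenly spread visits, same-day scan and EDSS, and 3% to 17% first detected at Week 96, the bias at Day 673 can be negligible or can exceed the planned 4-point half-width. Visits that run late increase it; a scan before the EDSS reduces it. At Day 687 with same-day assessments it exceeds 4 points throughout.

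The same dating rules apply to the first T1 and first T2 lesion curves, but no size was calculated for them. This should be corrected before the final analysis; it does not undermine the primary result.

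**What to change.** In SAP 4.4.2, for time to protocol-defined event, first T1 Gd lesion and first T2 lesion:

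1. After windowing, set MRI-detected event times and end-of-study censoring to the nominal visit day (169, 337 or 673), with events before censoring at ties.
2. Read the curve at Day 673, on the scale where the first infusion is Day 1. Day 672 on that scale drops every Week 96 event.
3. Say how a relapse with onset after Day 673 but before a late Week 96 visit is handled, and treat it as in the primary analysis.
4. In the composite, count discontinuation for lack of efficacy or death as an event, as SAP 4.4.1 does. Remaining differences from the primary would then reflect the handling of dropouts.

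An interval-censored (Turnbull) estimate is an optional alternative to step 1. If Module 2 already does this, a sentence in the SAP saying so is enough.

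The cost is a few lines of SAP text and a change to how the time variable is derived, with no new data. The downside is that MRI-detected events lose their exact calendar dates in the Kaplan-Meier plot.
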